# Study Protocol and Statistical Analysis Plan

The present study recruited children suffering from SAR during the pollen season. They had a poor control of SAR despite antihistaminic treatment (cetirizine 2.5 mg bid in preschoolers or 5 mg bid in schoolers). SAR diagnosis was performed according to validated criteria. Allergy was defined if nasal symptom history was consistent with documented sensitization.

Inclusion criteria were: age range 4-12 years, SAR diagnosis, Total Symptoms Score (TSS)  $\geq$  6, and written informed consent of both parents or legal guardians. Exclusion criteria were: perennial AR, rhinitis due to other causes, concomitant acute or chronic rhinosinusitis, nasal polyps, asthma comorbidity, current use of topical or systemic corticosteroids, antihistamines, antileukotrienes, inadequate washout of them, nasal anatomic defect, respiratory infections in the last two weeks, participation in other clinical studies in the previous month, documented hypersensitivity to the study product or its excipients, and trip planned outside of the study area.

The study was conducted in a third-level pediatrics department located in Southern Italy. The study procedure was approved by the local Ethics Committee (Prt n 408, 20/06/2019).

Children were randomly (ratio 1:1) subdivided into two groups: the active group treated with MFNS (Mometasone group) and the control group treated with isotonic saline. For both groups, the schedule was for one spray into each nostril (MFNS 50 mcg/spray) twice a day for 21 days.

The participants were evaluated at baseline (T0), after 7 (T1) and 21 (T2) days, and 30 days (T3) after treatment discontinuation.

During the study, systemic or intranasal antihistamines, other corticosteroids, leukotriene antagonists, and sodium cromoglicate were prohibited.

The primary endpoint of this study was the change in eosinophilic infiltrate, assessed by nasal cytology, after the treatment. The secondary objectives were the nasal mast cell and neutrophil count, symptom severity, and QoL changes during the study.

Nasal cytology is a well-defined methodology. The procedure included sampling, processing, and microscope reading. Sampling required collecting cells from the surface of the middle portion of the inferior turbinate by a sterile disposable curette. The procedure was performed under anterior rhinoscopy, with an appropriate light source, and it was painless. The sample obtained was immediately smeared on a glass slide, air-dried, and stained with May-Grünwald-Giemsa (MGG) for 30 minutes. Next, the stained sample was read at optical microscopy, with a 1000x objective with oil immersion. The count of eosinophils, neutrophils, and mast cells was expressed as a mean of 10 microscopic fields.

The validated Pediatric Rhinoconjunctivitis Quality of Life Questionnaire (PRQLQ) consists of 23 questions in 5 domains (nasal symptoms, ocular symptoms, practical issues, limitation of activities, other symptoms) that are answered on a 7-point scale (0-6), where 0 represents the absence of problems and 6 the greatest symptom distress. Children will complete the questionnaire together with a parent at baseline and during the study. A Total Score was calculated as the mean of the 5 domains.

Total symptom score was the sum of 3 domains: i) nasal symptoms (TNSS) included itching, sneezing, rhinorrhea, nasal congestion; ii) ocular symptoms (TOSS): itching, hyperemia of the conjunctiva, tearing; and iii) throat symptoms (TTSS): itching, coughing. With the help of their parents, patients scored symptoms severity on a 4-point scale: 0 = absent or irrelevant, 1 = mild, 2 = moderate, 3 = severe. Total symptom score was assessed at 12 hours (TTS 12h) and two weeks (TTS 2W) before the visits. TSS represents the doctor's point of view of symptom severity.

A visual analogic scale (VAS) measured the parental perception of symptom severity (0=no symptom; 10=very severe symptoms).

Safety was assessed on the incidence of adverse events for each treatment and physical examination.

The statistical analysis included different tests. Shapiro-Wilk test was performed to investigate continuous variables distribution. Differences between the active and control group were tested with Mann-Whitney U test for independent samples. Longitudinal changes for continuous variables were investigated by Wilcoxon signed-rank test for paired samples. Delta changes in questionnaires scores were calculated for each group as T1-T0 scores for the control group, T2-T0 scores, and T3-T0 scores for the mometasone group. Differences in delta changes between groups were investigated by Mann-Whitney U test. Chi-square test and Fisher exact test were performed for differences in categorical variables. A  $p \leq 0.05$  was considered statistically significant. Data were expressed as median (interquartile range) or as a percentage as appropriate. All analyses were performed with SAS® on Demand for Academics (Cary, NC: SAS Institute Inc.)

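### The two-week symptom score at T1 (day 7) mixes the first treatment week with the week before it, and so understates the day-7 effect

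*Combined protocol and SAP*

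**What the plan says.** All the relevant text is in the combined protocol and SAP, under its single main heading.

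- **Look-back periods** (paragraph on the total symptom score): "Total symptom score was assessed at 12 hours (TTS 12h) and two weeks (TTS 2W) before the visits". No visit is exempted.
- **Visits** (design paragraphs): "The participants were evaluated at baseline (T0), after 7 (T1) and 21 (T2) days, and 30 days (T3) after treatment discontinuation".
- **Treatment length** (design paragraphs): dosing is "twice a day for 21 days". The day of the first dose is not given.
- **Role of the score** (endpoint paragraph): "The secondary objectives were the nasal mast cell and neutrophil count, symptom severity, and QoL changes during the study".
- **Tests** (statistical analysis paragraph): "Differences between the active and control group were tested with Mann-Whitney U test for independent samples", and "Longitudinal changes for continuous variables were investigated by Wilcoxon signed-rank test for paired samples". Neither sentence is limited to particular visits or to one version of the symptom score.

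**The concern.** A two-week look-back does not fit between two visits one week apart. At T1 it reaches back past T0 into the untreated period, over days that the family has already rated at T0. The T1 value is then part first treatment week and part baseline.

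What is at stake is how the T1 result is read. A reader will naturally take a symptom comparison at the 7-day visit as the effect of one week of treatment. If it comes from the two-week score, a real early effect will look smaller than it is and may be missed.

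**Working it through.** The plan states no window, overlap or dilution figure, so there is nothing of its own to reproduce. The check is interval arithmetic on the stated visit days.

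**Inputs.** T0 = day 0, T1 = day 7, T2 = day 21 and a 14-day look-back, all from the plan. T3 = 21 + 30 = day 51, assuming treatment ends on day 21. Dosing from T0 is assumed; a 21-day course with T2 at day 21 fits this but does not prove it.

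**Windows.** The window at visit day v runs from v − 14 to v.

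| Visit | Window (days) | Before treatment | On treatment | After treatment | Shared with T0 |
|---|---|---|---|---|---|
| T0 | −14 to 0 | 14 | 0 | 0 | – |
| T1 | −7 to 7 | 7 | 7 | 0 | 7 |
| T2 | 7 to 21 | 0 | 14 | 0 | 0 |
| T3 | 37 to 51 | 0 | 0 | 14 | 0 |

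T0 and T1 are the only pair of visits whose windows overlap.

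**Sensitivity to the first-dose day.** Let dosing start s days after T0, with s = 1, 2 or 3.

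- T1 counted from the first dose: the window is s − 7 to s + 7. Pre-treatment days are s − (s − 7) = 7. Days shared with T0 are 7 − s = 6, 5 or 4.
- T1 kept at day 7 after T0: pre-treatment days are 7 + s = 8, 9 or 10, and 7 are shared.

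Whether the visit day and the first-dose day are counted also moves the total slightly. Conventions giving 6 to 8 pre-treatment days leave 8/14 = 57% to 6/14 = 43% of the effect with equal weights and immediate onset.

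**Share of the full effect at T1.** The plan has no rule for how a family combines 14 days into one score, so every weighting here is an assumption. These figures use 7 pre-treatment and 7 treated days.

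- Equal weights, immediate onset: 7/14 = 50%.
- Equal weights, linear build-up over 7 days: with k/7 on treated day k, the sum is 28/7 = 4, and 4/14 = 29%. With (k − 0.5)/7, the sum is 24.5/7 = 3.5, and 3.5/14 = 25%.
- Recency weights 0.5^(lag/h), half-life h from 2 to 7 days: 92% to 67% with immediate onset, and 69% to 37% with the 7-day build-up (both day conventions).

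Part of the loss in the build-up case is ordinary averaging of a growing effect. Relative to the mean effect over the first treatment week, equal weighting always halves it: the means are 4/7 = 57% and 3.5/7 = 50%, and the T1 score carries 29% and 25%.

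**Change from T0.** With equal weights the 7 shared days cancel, so T1 − T0 = ½ × (mean of the week after T0 − mean of the earlier week of the T0 window).

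**Validity.** Both arms use the same window. With no treatment effect, randomisation leaves their T1 scores exchangeable, so the Mann-Whitney test keeps its level. A simulation under assumed conditions (30 per arm, day-to-day autocorrelation 0.9, 5,000 runs) gave 5.1% rejections at 0.05.

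**The case against.** The plan never says that the two-week score at T1 measures one week of treatment. It names only change in symptom severity during the study as a secondary objective, and it already provides a 12-hour version and a visual analogue scale. That a T1 test on the two-week score will be run is inferred from analysis sentences that are general rather than specific. The retained share runs from 25% to 92% depending on weights and onset that the documents do not give, so a large loss is possible but not shown. Making the T1 value descriptive also sets aside a comparison that is valid under no effect.

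Most of this stands, and it limits the size of the point. It does not remove it. Nothing exempts T1, the tests cover it as written, and every recall scenario above gives less than the full effect.

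A reader might infer four stronger things, which the documents do not support:

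- *That T1 carries no treatment information.* On the recall reading with dosing from T0, the window contains the whole first treatment week.
- *That T1 is wholly pre-treatment.* The literal wording allows a single point two weeks before each visit (days −14, −7, 7 and 37). Paired with a 12-hour version, a recall period is the more natural sense. This supports a request to confirm, not a finding.
- *That the between-arm test is invalid.* It is diluted, not biased under no effect.
- *That the planned deltas are affected.* The plan says "Delta changes in questionnaires scores were calculated for each group as T1-T0 scores for the control group, T2-T0 scores, and T3-T0 scores for the mometasone". It does not say whether those questionnaire scores include the two-week symptom score, so nothing here rests on that sentence.

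**Conclusion.** The point holds as a minor one. On the recall reading with dosing from T0, half of the T1 window (7 of 14 days) precedes treatment and repeats days already rated at T0. If T1 is counted from a first dose 1 to 3 days after T0, 7 days are still pre-treatment and 4 to 6 are shared. The two-week score at T1 and its change from T0 therefore understate the day-7 effect: about 50% is retained with equal weights and immediate onset, 25% to 29% with a 7-day build-up, and more if recent days dominate recall.

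The window arithmetic is firm given the visit days and the dosing assumption. The percentages are illustrations. The scope is one version of one secondary outcome at one visit.

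**What to change.** - Use the 12-hour score as the symptom measure for the day-7 comparison.
- Base the on-treatment analysis of the two-week score on T2 versus T0, where the window is wholly on treatment.
- Treat T3 versus T0 as a post-treatment persistence analysis, since its window lies entirely after treatment.
- Report the two-week score at T1 as descriptive, state the overlap with T0, and do not interpret it as the one-week effect.
- State the day of the first dose, the day from which T1 is counted, whether the T1 − T0 delta includes the two-week score, and that this score is a 14-day recall. If it is instead a single point 14 days earlier, T1 is wholly pre-treatment and T2 refers to day 7, and the labels must say so.

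This changes analysis and reporting text only, because the 12-hour score is already collected. The cost is that the formal day-7 symptom comparison rests on a 12-hour snapshot, and a valid though diluted comparison loses its inferential role.

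### No between-arm comparison of a continuous outcome, including primary eosinophils, conditions on the T0 value already collected; the cost is precision, not validity

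*Combined protocol and SAP*

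**What the plan says.** The statistical paragraph that closes the Combined protocol and SAP is the whole analysis plan. It names two between-arm procedures for continuous outcomes:

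- A general one: "Differences between the active and control group were tested with Mann-Whitney U test for independent samples". It does not say which quantity is compared or at which visit.
- One for change scores: "Differences in delta changes between groups were investigated by Mann-Whitney U test". Changes are defined for questionnaire scores only, with visits that differ by arm: "Delta changes in questionnaires scores were calculated for each group as T1-T0 scores for the control group", but T2-T0 and T3-T0 for mometasone.

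The other use of T0 is a paired test: "Longitudinal changes for continuous variables were investigated by Wilcoxon signed-rank test for paired samples". Chi-square and Fisher tests cover categorical variables. Results are summarised descriptively: "Data were expressed as median (interquartile range) or as a percentage as appropriate". No treatment-effect estimate or confidence interval is mentioned.

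The design text (*Study Protocol and Statistical Analysis Plan*) says: "The primary endpoint of this study was the change in eosinophilic infiltrate, assessed by nasal cytology, after the treatment". T0 is a scheduled visit: "The participants were evaluated at baseline (T0), after 7 (T1) and 21 (T2) days". Allocation is 1:1, with no stratification by baseline named.

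**The concern.** The primary endpoint is a change, yet the plan does not say whether the eosinophil count or its change is compared between arms. The gap exists either way. A test on follow-up values ignores T0. A test on raw change subtracts T0 with a slope fixed at 1, which is not the same as conditioning on it. The paired Wilcoxon test uses T0 but works within an arm and does not compare arms.

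Two things are at stake: avoidable noise in the primary comparison, and a treatment contrast that moves with any chance difference between the arms at T0. Both can be reduced without another child or visit.

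**Working it through.** **Inputs.** From the documents: the tests named, 1:1 allocation, the 0.05 threshold, T0 as a scheduled visit, and counts expressed as a mean of 10 fields. The documents give no N, SD, effect size or T0-to-follow-up correlation ρ, so there is no planned figure to reproduce. *Assumed:* 30 per arm, two-sided 5%, effect 0.6 SD, ρ = 0.3/0.5/0.7; counts lognormal (median 5, log SD 0.8), rounded to 0.1. Triplets below follow that order of ρ.

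**1. Inventory.** Two between-arm procedures for continuous outcomes, both unadjusted Mann-Whitney; none conditions on T0.

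**2. Variance.** With equal SDs, relative variances are 1 for follow-up, 2(1−ρ) for raw change and 1−ρ² after linear adjustment. Sample size needed relative to adjustment:

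- follow-up, 1/(1−ρ²): 1.10/1.33/1.96
- raw change, 2(1−ρ)/(1−ρ²): 1.54/1.33/1.18

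**3. Power for counts, separating T0 from the change of test.** Moving from Mann-Whitney to log-scale ANCOVA changes two things, so T0 is credited only within one scale.

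| Analysis of follow-up | Equal ρ | Active-arm ρ = 0 |
|---|---|---|
| Unadjusted t-test on logs | .620/.633/.632 | .636/.624/.628 |
| ANCOVA on log(count+0.1) | .661/.742/.887 | .638/.650/.672 |
| *T0 gain, log scale (points)* | *4.1/10.9/25.5* | *0.2/2.6/4.4* |
| Mann-Whitney | .600/.600/.599 | .597/.604/.605 |
| Rank ANCOVA | .634/.710/.847 | .608/.624/.653 |
| *T0 gain, rank scale (points)* | *3.4/11.0/24.8* | *1.1/2.0/4.8* |

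The log rows use 3,000 replicates and the rank rows 10,000. A separate log-scale run gave about 3/12/27 and 0/3/6. Overall: about 3–4/12/26 points with equal correlation, and about 0–1/3/5–6 if treatment breaks it.

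Mann-Whitney on the raw change in counts, a literal reading of the primary endpoint, had power .350/.463/.664. That is below the follow-up test at ρ = 0.3 and 0.5, and above it at 0.7.

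**4. Large effect.** At 1.2 SD, Mann-Whitney on follow-up is .993 and log ANCOVA .997–1.000, so there is almost nothing to gain.

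**5. Type I error.** Rejection under the null was .043–.055 for all methods. The planned tests are valid on average over randomisations.

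**6. Chance imbalance.** Its SD is √(2/30) = 0.26 SD. A 0.3 SD imbalance shifts a follow-up comparison by 0.3ρ = 0.09/0.15/0.21 SD, and a change comparison by 0.3(ρ−1) = −0.21/−0.15/−0.09 SD. Given a 0.4 SD imbalance (normal data, no effect), rejection was .056/.076/.104 on values and .103/.073/.070 on changes, against .048–.052 for ANCOVA.

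**7. Questionnaires.** For PRQLQ (assumed mean 2.5, SD 1), Mann-Whitney had power .591/.590/.598 on follow-up and .462/.596/.814 on the change at a matched visit. Rank ANCOVA had .630/.703/.850. Against the better unadjusted test: .630−.591, .703−.596 and .850−.814, or about 4/11/4 points.

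**8. Zeros in the counts.** For Poisson totals over 10 fields with a true rate ratio of 0.49, the log(count+0.1) model's ratio averaged 0.58 with 14% zeros and 0.69 with 38%. The constant matters: with 43% zeros, constants 0.01/0.1/0.5 gave 0.50/0.72/0.87. At 43% zeros and equal ρ, T0 added only about 1/3/6 points on ranks and 0/3/7 on logs.

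**The case against.** **The planned tests are valid, and every size is assumed.** Both are true. Nothing in the documents places this trial within a range that runs from almost no gain to a large one. What remains is that adjustment uses data already collected and costs little.

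**Setting Mann-Whitney against log ANCOVA overstates what T0 does.** This stands. A reader making that comparison might infer a gain of about 6/14/28 points. Some 2–3 points of each come from replacing a rank test with a parametric test on data simulated to suit it.

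**The log model does not estimate a ratio of counts.** This also stands. It estimates a ratio of geometric means of (count+0.1), which depends on the constant when zeros are common. The documents give no zero frequency for any cell type.

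**An effect estimate does not need ANCOVA.** Correct: a Hodges-Lehmann estimate with a confidence interval could accompany the planned test.

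**It may be too late.** The text is mostly in the past tense. If results by arm are known, an adjusted analysis cannot replace the planned one.

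Two stronger readings are tempting. A reader might infer that the unadjusted tests inflate the false-positive rate. Step 5 shows they do not overall; the excess in step 6 is conditional on an imbalance having occurred. A reader might also infer that the primary endpoint is judged only by within-arm tests. The general Mann-Whitney sentence can cover eosinophils; it simply does not name them.

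**Conclusion.** The point holds as a matter of efficiency and robustness: the plan conditions no between-arm comparison of a continuous outcome on T0, and this includes the primary endpoint. It is not a finding that the tests are invalid. The gains in step 3 rest on 30 per arm, a 0.6 SD effect and few zeros; they shrink when zeros are frequent, when treatment breaks the correlation or when the effect is large. The change is worth making because it is cheap, not because a large benefit has been shown.

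The validity statement applies to comparisons at a common visit. The questionnaire changes as written set T1-T0 in control against T2-T0 and T3-T0 in mometasone. That is a separate problem, which adjustment for T0 does not repair.

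**What to change.** - **Visit.** For each comparison, name one post-baseline visit, the same in both arms.
- **TSS, VAS, PRQLQ.** Make the between-arm analysis an ANCOVA on the follow-up score with T0 as covariate, and report the adjusted difference with 95% CI.
- **Eosinophils (primary), mast cells, neutrophils.** Fix in advance one T0-adjusted test: either rank ANCOVA, which needs no added constant, or ANCOVA on log(count+0.1) with T0 on the same scale. If the log model is chosen, describe its estimate as a ratio of geometric means of (count+0.1), state that it is pulled towards 1 when zeros are common, and show results for other constants.
- **Planned test.** Always report the Mann-Whitney test alongside, with no data-driven switch between analyses.
- **Timing.** Fix these choices before results are seen by arm. If that point has passed, report the adjusted analysis labelled post hoc beside the planned test.
- **Change scores.** Reconcile the visit definitions separately.

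The cost is a few sentences in the SAP and slightly more analysis in the SAS software already named, with no new data. The drawback of rank ANCOVA is that it gives no estimate in cells per field.

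### The plan ties no between-arm comparison, visit or use of the T0 count to the primary eosinophil endpoint; it should name one T2 comparison adjusted for T0

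*Combined protocol and SAP*

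**What the plan says.** All the text is in the combined document, section Study Protocol and Statistical Analysis Plan.

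- **Design.** "Children were randomly (ratio 1:1) subdivided into two groups": mometasone spray or isotonic saline, for 21 days.
- **Visits.** "The participants were evaluated at baseline (T0), after 7 (T1) and 21 (T2) days, and 30 days (T3) after treatment discontinuation".
- **Primary endpoint.** "The primary endpoint of this study was the change in eosinophilic infiltrate, assessed by nasal cytology, after the treatment". No visit is named.
- **Cytology.** "The procedure included sampling, processing, and microscope reading", and "The count of eosinophils, neutrophils, and mast cells was expressed as a mean of 10 microscopic fields". The visits at which samples were taken are not given.
- **Statistical paragraph, between arms.** "Differences between the active and control group were tested with Mann-Whitney U test for independent samples". No variable, visit or scale (count or change) is named.
- **Statistical paragraph, over time.** "Longitudinal changes for continuous variables were investigated by Wilcoxon signed-rank test for paired samples".
- **Statistical paragraph, deltas.** "Delta changes in questionnaires scores were calculated for each group as T1-T0 scores for the control group"; the same sentence then lists T2-T0 and T3-T0 for the mometasone group. A Mann-Whitney test of deltas between groups follows.

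The statistical paragraph does not mention eosinophils, cytology or the primary endpoint. It sets the threshold at p ≤ 0.05 without saying whether tests are two-sided. No sample size, SD or between-visit correlation is given.

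**The concern.** A randomised trial answers its primary question with a comparison between arms. Here a reader cannot tell from the plan which comparison that is. Three things are open: which test between arms applies to eosinophils, at which visit, and how the T0 count enters, although an endpoint defined as a change needs T0 in some form.

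Two consequences follow. First, if the general Mann-Whitney test is applied to post-treatment counts, it discards baseline information that the trial must already hold, and power is lost. Second, if cytology was done at both T2 and T3, either result could be presented as the answer, and the chance of a false positive rises above the nominal 5%.

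**Working it through.** **Step 1. Match each test to the endpoint.**

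| Sentence in the statistical paragraph | Reaches eosinophils? | Compares arms? | Uses T0? | Names a visit? |
|---|---|---|---|---|
| General Mann-Whitney | Yes, by its general wording | Yes | No, when applied to counts | No |
| Paired Wilcoxon on longitudinal change | Yes, plainly | No | Yes | No |
| Delta rule and its Mann-Whitney | Not as written: delta is defined for questionnaire scores | Yes | Yes | Yes, but different visits by arm |

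No row gives a between-arm comparison that uses T0 at one named visit for the primary endpoint.

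**Step 2. Which visit?** Treatment lasts 21 days. T1 (day 7) is during treatment. T2 (day 21) is its end, and T3 is 30 days after stopping. T2 is the natural reading; T3 also falls after treatment and nothing excludes it.

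**Step 3. Power lost by ignoring T0.** There is no figure in the plan to reproduce. Assumed inputs: 30 per arm, true effect 0.6 SD at T2, T0-T2 correlation ρ = 0.3, 0.5 or 0.7, two-sided 5%.

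Hand approximation for normal data:
- Mann-Whitney on the T2 count: 0.6 × √(30/2) × √(3/π) = 2.324 × 0.977 = 2.271; power ≈ Φ(2.271 − 1.96) = Φ(0.311) = 62%.
- Adjusted for T0: divide by √(1 − ρ²). This gives 2.271/0.954 = 2.381, 2.271/0.866 = 2.622 and 2.271/0.714 = 3.180; power ≈ Φ(0.421) = 66%, Φ(0.662) = 75% and Φ(1.220) = 89%.

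Simulation, 10,000 replicates per setting. Rank analysis of covariance regresses the T2 ranks on arm and the T0 ranks. Entries are power (%) at ρ = 0.3 / 0.5 / 0.7:

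| Data | Mann-Whitney, T2 count | Mann-Whitney, raw T2-T0 change | Rank ANCOVA | Gain, ANCOVA over T2 count (points) |
|---|---|---|---|---|
| Normal | 60.2 / 59.6 / 61.2 | 46.0 / 59.6 / 81.7 | 63.7 / 71.1 / 85.6 | 3.5 / 11.5 / 24.4 |
| Lognormal, log-SD 1 | 60.6 / 60.4 / 59.2 | 34.2 / 44.1 / 62.0 | 64.5 / 71.3 / 84.5 | 3.9 / 10.9 / 25.3 |
| Skewed counts with ties, 14-26% zeros at T2 | 44.7 / 44.4 / 43.4 | 10.7 / 11.8 / 11.3 | 46.9 / 50.2 / 56.9 | 2.2 / 5.8 / 13.5 |

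In the count row, ρ and the 0.6 apply to the latent log rate. With no true effect, all three tests reject in 4.5-5.5% of runs.

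**Step 4. False positives if either T2 or T3 could be reported.** This assumes that cytology was done at both visits. For two independent tests the rate is 1 − 0.95² = 9.75%. For correlated visits (ρ 0.3-0.7, 20-50 per arm, 20,000 replicates, Mann-Whitney on counts) it is 8.0-9.4%, against 4.6-5.1% at T2 alone.

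**Step 5. What a rank effect estimates when counts tie.** With N children in total, θ = 0.5 + (adjusted mean rank on saline − adjusted mean rank on mometasone)/N. This is P(lower count on mometasone) + ½ P(tie), not P(lower) alone. In the count model above, P(lower) = 0.57 and P(tie) = 0.12, so θ = 0.57 + 0.06 = 0.63. In a sparser version (24-38% zeros), 0.53 + 0.18/2 = 0.62. The definition therefore has to include the tie term. An untransformed interval can also pass 1: with normal data, 30 per arm and an assumed effect of 2 SD, the upper limit did so in 51-80% of runs.

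**The case against.** The strongest reply is that the general Mann-Whitney sentence has no restriction on variables, so it covers eosinophils, and that T2 is obviously the visit meant. Much of this stands. A reader might infer that the plan has no between-arm test of its primary endpoint, or an invalid one; the text does not support that. The test exists and holds its 5% level. What remains is that it is not tied to the endpoint or to a visit and, on counts, does not use T0.

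A reader might also infer that efficacy would be claimed from a significant fall on mometasone and a non-significant one on saline. The plan states no such rule. Nor does it say that eosinophil change was taken at different visits in the two arms; that delta rule is confined to questionnaire scores. And it does not say that cytology was done at T3, so the 8-9% figure is conditional.

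A further reply is that one Mann-Whitney test on T2-T0 change would close the gap with the plan's own methods. It would, and it is valid. But in every setting of step 3 it has less power than the baseline-adjusted analysis; at ρ = 0.3 it falls below the T2 count alone, and on tied counts it reaches only 11-12%. Rank analysis of covariance is one suitable adjusted method, not the only one.

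**Conclusion.** The point holds as a gap in specification together with an avoidable loss of efficiency. The plan ties no between-arm comparison, visit or use of T0 to its primary endpoint, and its available between-arm test of counts is valid but unadjusted. It should be fixed, but no result is wrong because of it.

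The gain from adjustment is about 4, 11 and 25 points for continuous data as correlation rises from 0.3 to 0.7, and about 2 to 14 points for skewed, tied counts. These sizes rest wholly on assumed sample size, effect, correlation and distribution. The textual gap does not depend on them.

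**What to change.** State one primary comparison: eosinophil count at T2, mometasone versus saline, adjusted for the T0 count (for example by rank analysis of covariance), two-sided 5%. In addition:

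- Make T1 and T3 secondary. Label the paired Wilcoxon tests descriptive, supporting no efficacy claim.
- State the cytology visits. If none was at T2, name the one post-treatment visit used, the same in both arms.
- Show medians (IQR) by arm and visit.
- If the rank effect is reported, define it as the baseline-adjusted P(lower count on mometasone) plus half P(tie), and keep its confidence interval within 0 to 1, for example on a logit scale.
- Do not apply the questionnaire delta rule to cell counts.

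The cost is one further analysis of counts that a change endpoint already requires (assuming cytology at T0 and T2), plus wording. The gain is small if the baseline correlation is low, and the rank effect is less familiar than a difference in cells per field, so the medians should sit beside it. The document is written in the past tense, so the analysis may have to be labelled as not pre-specified.

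### Within-arm signed-rank tests of the symptom score used for entry can show significant improvement from regression to the mean alone, so they should be descriptive

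*Combined protocol and SAP*

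**What the plan says.** The eligibility paragraph of the combined protocol and SAP opens with "Inclusion criteria were: age range 4-12 years, SAR diagnosis, Total Symptoms Score (TSS"; the threshold that follows is 6 or more. Children were also recruited because of severity: "They had a poor control of SAR despite antihistaminic treatment". The visit schedule begins at T0: "The participants were evaluated at baseline (T0), after 7 (T1) and 21 (T2) days, and 30 days (T3) after treatment discontinuation". No screening visit or repeat baseline is listed.

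The endpoint paragraph makes change over time in symptoms and quality of life a secondary aim: "The secondary objectives were the nasal mast cell and neutrophil count, symptom severity, and QoL changes during the study". The primary endpoint is the change in eosinophils on nasal cytology.

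The statistical paragraph plans within-arm tests for every continuous variable ("Longitudinal changes for continuous variables were investigated by Wilcoxon signed-rank test for paired samples") at p of 0.05 or less, with no exception for the entry score. It also plans between-arm tests: "Differences between the active and control group were tested with Mann-Whitney U test for independent samples". The same test is applied to delta changes in the questionnaire scores. As written, those deltas are T1-T0 for the control group and T2-T0 and T3-T0 for the mometasone group.

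**The concern.** When a child must score 6 or more to enter, some enter because the score happened to be high that day. If that same score serves as T0, the next measurement is expected to be lower with no treatment at all. The signed-rank hypothesis of no shift is then false because of the entry rule, in the saline arm as much as in the mometasone arm. VAS and PRQLQ are affected to the extent that they correlate with TSS.

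At stake is how the results are read. A significant paired fall in one arm is easily reported as improvement on treatment, and a significant fall in one arm with a non-significant fall in the other is easily taken as a difference between treatments. Neither inference is sound for a score used to select the children.

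**Working it through.** **1. Inputs from the documents.** Entry cut: 6. Score range: "Total symptom score was the sum of 3 domains", with 4 nasal, 3 ocular and 2 throat items, each scored 0 to 3, so 9 x 3 = 27 and the range is 0 to 27. Significance level: 0.05, sidedness not stated and taken here as two-sided. The documents give no sample size, SD, visit-to-visit correlation or expected mean, so there is no planned figure to reproduce.

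**2. Assumptions.** Mean (mu) of candidates before the cut 6, 8, 10 or 13; SD 4; correlation between T0 and the later visit 0.6 (range 0.4 to 0.8); 40 children per arm (also 20). Mean and SD are the same at every visit, with no treatment effect and no time trend. The qualifying score is the T0 score. Scores are rounded to whole numbers and bounded at 0 and 27.

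**3. Expected fall.** For a normal score with cut c, let z = (c - mu)/SD and L = phi(z)/(1 - Phi(z)). The mean among those selected is mu + SD x L, and the expected fall is (1 - correlation) x SD x L. For whole-number scores, 6 or more corresponds to c = 5.5.

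At mean 8: z = (5.5 - 8)/4 = -0.625; phi = 0.3282; 1 - Phi = 0.7340; L = 0.447; SD x L = 1.79; fall = 0.4 x 1.79 = 0.72 points. (With c = 6 on a continuous scale the fall is 0.81; the conclusion is the same.)

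**4. Rejection rate.** Wilcoxon signed-rank within one arm, 40 children, correlation 0.6, by simulation:

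| Unselected mean | Share passing the cut | Expected fall (points) | Two-sided rejection |
|---|---|---|---|
| 6 | 55% | 1.15 | about 55% |
| 8 | 73% | 0.72 | about 25% |
| 10 | 87% | 0.39 | about 10% |
| 13 | 97% | 0.11 | about 5% |

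**5. Sensitivity.** Counting only significant improvement (nominal 2.5%), with correlation from 0.8 down to 0.4:

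| Unselected mean | 20 per arm | 40 per arm |
|---|---|---|
| 6 | 17% to 41% | 29% to 74% |
| 8 | 8% to 17% | 16% to 34% |
| 10 | 6% to 9% | 6% to 13% |
| 13 | about 3% to 4% | about 3% to 4% |

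**6. Between-arm comparison.** Under the same selection, the Mann-Whitney test on change at the same visit rejects in 3.8% to 6.1% of simulated trials. This is nominal within simulation error, because both arms regress alike. Taking control T1-T0 against mometasone T2-T0, as the delta sentence reads, the rate is 4.0% to 12.5%, highest at mean 6. That excess assumes that the correlation with T0 declines over time (T0-T2 correlation equal to the square of T0-T1). With equal correlations the expected fall in step 3 is the same at both visits and this excess goes. Any seasonal trend between the visits would still be mixed with treatment: day 7 for control against day 21, or day 21 + 30 = 51, for mometasone.

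**7. Separate qualifying score.** If eligibility were scored beforehand and T0 measured afresh (stable true level, independent error each time), within-arm rejection is 4.5% to 5.3%, which is nominal.

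**The case against.** Five arguments can be made on the other side.

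- **The plan already has randomised comparisons.** It does, and step 6 shows that they hold at a common visit. Nothing in the document says that efficacy will be claimed from the paired tests. This stands, and it limits the point to the within-arm p-values and the delta definition. The delta sentence may be a drafting slip, since both arms follow the same visit schedule, but as written it weakens that protection.
- **The cut may remove few children.** On a 0 to 27 scale, in poorly controlled children in season, a threshold of 6 could exclude almost nobody. The mean-13 row shows that inflation is then negligible. This also stands. A reader might infer that regression to the mean will by itself make both arms significant. The documents do not support that, because they give none of the quantities that decide it, and in several plausible settings the test is usually non-significant.
- **The qualifying score may not be T0.** Inadequate washout is an exclusion, so there may have been a gap before T0. The score also has two recall windows ("Total symptom score was assessed at 12 hours (TTS 12h) and two weeks (TTS 2W) before the visits"), and the criterion does not say which one applies. The visit list suggests that the qualifying score is T0 but does not state it.
- **Rejecting a false hypothesis of no shift is not a type I error.** This is correct. The rates in step 4 measure how often a real but treatment-unrelated shift would be declared significant. The fault lies in the interpretation, not in the test's arithmetic.
- **TSS is secondary, and VAS and PRQLQ were not modelled.** Both are true. A reader might extend the point to the primary analysis, but children are not selected on eosinophil count.

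**Conclusion.** The point holds in a limited form. If the qualifying TSS is the T0 score, within-arm signed-rank tests of TSS are biased towards improvement and cannot show a treatment effect in either arm. With SD 4, correlation 0.6 and 40 per arm, the two-sided rejection rate without any effect ranges from about 55% (unselected mean 6) to about 5% (mean 13). All these inputs are assumed, so the figures show a possible size and do not predict it. VAS and PRQLQ are affected less, by an amount not quantified here.

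The point does not invalidate the randomised comparison or touch the primary endpoint through selection. It bears on secondary conclusions, and on the delta comparison only because the arms are assigned different visits as written.

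**What to change.** 1. Report within-arm change in TSS, VAS and PRQLQ as median and interquartile range by visit, labelled as including regression to the mean, without significance tests.
2. Correct the delta definition so that T1-T0, T2-T0 and T3-T0 are calculated in both arms.
3. Base every symptom and QoL conclusion on the between-arm comparison at the same visit.
4. State whether the qualifying TSS is the T0 score, and which recall window the threshold applies to.

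This changes SAP and reporting text only and needs no new data. The downside is the loss of within-arm p-values that cannot be read as treatment effects.
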